**Table 9. List of Laboratory Variables (Continued)**

Laboratory Variables
Other
hs-CRP
QuantiFERON-TB Gold a
IgG and IgM
ESR

a. For annual follow-up, QFT is captured only for those with negative QFT at Screening.

### 10.3.2 Analysis of Laboratory Data for Period 1

The laboratory data will be summarized by the "as treated" treatment groups (upadacitinib 15 mg QD, upadacitinib 30 mg QD, and combined placebo groups) and overall.

#### 10.3.2.1 Assessment of Mean Change from Baseline in Clinical Laboratory Variables

Analyses of mean change from baseline in continuous hematology, chemistry, and urinalysis variables which are measured longitudinally will be performed by visits and by "as treated" treatment group. For each change from baseline analysis, the following summary statistics will be presented for each treatment group: sample size, baseline mean, visit mean, and the mean, standard deviation, and median of the changes from baseline. An ANOVA model with treatment as a factor will be used to test statistical significance for the change from baseline mean among different treatment groups.

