8.1.5 Safety Analyses

8.1.5.1 General Considerations

Safety analyses will be carried out using the Safety Analysis Set. Analyses will be conducted for Period 1 alone, as well as for Period 1 and Period 2 combined.

Safety analyses are based on treatments actually received. Safety will be assessed by AEs, physical examination, laboratory assessments, ECG, and vital signs. Frequency tables and lists of subjects with treatment-emergent AEs by preferred term as in the Medical Dictionary for Regulatory Activities (MedDRA) dictionary, by system organ class, by severity, and by relationship to the study drug as assessed by the Investigator will be provided. The changes from baseline in vital signs, physical examination results, and clinical laboratory values will be analyzed in a descriptive manner. Shift of laboratory values from baseline to defined time points will be tabulated.

Missing safety data will not be imputed.

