#### **4.2 Overall Study Design and Plan**

This is a Phase 3 multicenter study that includes two periods. Period 1 is a 12-week, randomized, double-blind, parallel-group, placebo-controlled period designed to compare

---

the safety and efficacy of upadacitinib 30 mg QD and 15 mg QD versus placebo for the treatment of signs and symptoms of subjects with moderately to severely active RA who are on a stable dose of csDMARDs and have an inadequate response to csDMARDs. Period 2 is a blinded long-term extension period to evaluate the long-term safety, tolerability, and efficacy of upadacitinib 30 mg QD and 15 mg QD in subjects with RA who have completed Period 1. Starting with Amendment 6, all subjects will receive open-label upadacitinib 15 mg QD, including those currently on upadacitinib 30 mg QD.

The study is designed to enroll approximately 600 subjects at approximately 230 study centers worldwide to meet scientific and regulatory objectives without enrolling an undue number of subjects in alignment with ethical considerations. Therefore, if the target number of subjects has been enrolled, there is a possibility that additional subjects in screening will not be enrolled.

The study duration includes a 35-day screening period; a 12-week randomized, double-blind, parallel-group, placebo controlled treatment period (Period 1); a 248-week blinded long-term extension period (Period 2); and a 30-day follow-up period (call or visit).

Subjects who meet eligibility criteria will be randomized in a 2:2:1:1 ratio to one of four treatment groups:

- Group 1: Upadacitinib 30 mg QD, N = 200 (Period 1) → Upadacitinib 30 mg QD (Period 2)
- Group 2: Upadacitinib 15 mg QD, N = 200 (Period 1) → Upadacitinib 15 mg QD (Period 2)
- Group 3: Placebo, N = 100 (Period 1) → Upadacitinib 30 mg QD (Period 2)
- Group 4: Placebo, N = 100 (Period 1) → Upadacitinib 15 mg QD (Period 2)

Randomization is stratified by prior exposure to bDMARD (yes/no) and geographic region.

Subjects must have been on a stable dose of csDMARD(s) for  $\geq 4$  weeks prior to the first dose of study drug and must remain on a stable dose until Week 24; the csDMARD dose may be decreased only for safety reasons.

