### **9.2.3 Key Secondary Efficacy Analyses**

Ranked key secondary endpoints (at Week 12) for US/FDA regulatory purposes are:

1. Change from baseline in DAS28 (CRP);
2. Change from baseline in HAQ-DI;
3. Change from baseline in Short Form-36 (SF-36) Physical Component Score (PCS);
4. Proportion of subjects achieving LDA based on  $\text{DAS28 (CRP)} \leq 3.2$ ;
5. Proportion of subjects achieving Clinical remission (CR) based on DAS28 (CRP);
6. Proportion of subjects achieving LDA based on  $\text{CDAI} \leq 10$ ;
7. Change from baseline in morning stiffness (duration);
8. Change from baseline in Functional Assessment of Chronic Illness Therapy-Fatigue (FACIT-F).

Ranked key secondary endpoints (at Week 12) for EU/EMA regulatory purposes are:

1. Change from baseline in DAS28 (CRP);
2. Change from baseline in HAQ-DI;
3. ACR20 response rate;
4. Change from baseline in Short Form-36 (SF-36) Physical Component Score (PCS);
5. Proportion of subjects achieving Clinical remission (CR) based on DAS28 (CRP);
6. Proportion of subjects achieving LDA based on CDAI  $\leq$  10;
7. Change from baseline in morning stiffness (duration);
8. Change from baseline in Functional Assessment of Chronic Illness Therapy Fatigue (FACIT-F).

Other key secondary endpoints (at Week 12) for both US/FDA and EU/EMA regulatory purposes are:

1. ACR50 response rate;
2. ACR70 response rate;
3. Proportion of subjects achieving ACR20 response rate of Week 1.

For binary endpoints, frequencies and percentages will be reported for each randomized treatment group. Similar analyses as for the primary endpoint will be conducted.

For the major RA continuous endpoints DAS28 and HAQ-DI change from baseline, statistical inference will be conducted using analysis of covariance (ANCOVA) coupled with MI for missing data handling. Specifically, the ANCOVA model will include treatment as the fixed factor, and the corresponding baseline value and the stratification factor prior bDMARD use (Yes/No) as the covariates. For other continuous endpoints, statistical inference will be conducted using the MMRM model as described in

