### **9.2.5 Handling of Multiplicity**

[figure not shown]
The overall type I error rate of the primary and ranked key secondary endpoints for the two doses will be strongly controlled using a graphical multiple testing procedure. Specifically, the testing will utilize the endpoint sequence of primary endpoint followed by the ranked key secondary endpoints in the order as specified in Section 9.2.3, and will begin with testing the primary endpoint using  $\alpha$  of 0.025 for each dose. Continued testing will follow a pre-specified  $\alpha$  transfer path which includes downstream transfer along the endpoint sequence within each dose as well as cross-dose transfer. Adjusted p-values for the primary and ranked key secondary endpoints will be provided based on the testing procedure.

The graphs for the testing procedures are provided in Figure 3 and Figure 4, for US/FDA and EU/EMA regulatory purposes respectively. In the graph, the arrows specify the  $\alpha$  transfer paths. Once an endpoint is rejected (i.e., deemed significant) at its assigned significance level, its significance level will be transferred to subsequent endpoint(s) following the arrow(s). If more than one arrow originates from an endpoint, the significance level for this endpoint (once rejected) will be split between multiple subsequent endpoints following the arrows. The numbers on the arrows denote the weights for transferring and (possibly) splitting significance levels. Specifically, the

[figure not shown]
weight 1 denotes 100% transfer of significance level, and the weight  $\frac{1}{2}$  denotes 50 – 50% splitting of significance level.

In addition, the last two endpoints in the graph, which are change from baseline in FACIT-F for high dose and low dose, will be tested in sequence at  $\alpha = 0.05$  after all previous endpoints in both doses are deemed significant.

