**Table 10. Criteria for Potentially Clinically Significant Vital Sign Findings**

Vital Sign	Category	Criteria for Potential Clinically Significant Vital Signs
Systolic blood pressure	Low	Value $\leq$ 90 mmHg and decrease $\geq$ 20 mmHg from Baseline
	High	Value $\geq$ 160 mmHg and increase $\geq$ 20 mmHg from Baseline
Diastolic blood pressure	Low	Value $\leq$ 50 mmHg and decrease $\geq$ 15 mmHg from Baseline
	High	Value $\geq$ 105 mmHg and increase $\geq$ 15 mmHg from Baseline
Weight	High	> 7% increase from baseline
	Low	> 7% decrease from baseline

#### 10.4.2 Analysis of Vital Sign for Period 1

Analyses of mean change from baseline in continuous vital sign variables which are measured longitudinally will be performed by visits and by the "as treated" treatment groups of upadacitinib 15 mg QD, upadacitinib 30 mg QD, and combined placebo groups. For each change from baseline analysis, the following summary statistics will be presented for each treatment group: sample size, baseline mean, visit mean, and the mean, standard deviation, and median of the changes from baseline. An ANOVA model with treatment as factor, will be used to test statistical significance for the change from baseline mean among different treatment groups.

The number and percentage of subjects meeting the criteria for potentially clinically significant vital sign values will be summarized by "as treated" treatment group and overall.

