## 11.0 Summary of Changes

### 11.1 Summary of Changes between the Previous Version and the Current Version

The primary efficacy analysis and Period 1 reporting have been completed under the SAP version 2.0. The current SAP update applies only to future reporting of long-term analysis.

1. Updated throughout the SAP to align with Protocol Amendment 6, 7, and 8 including handling of dose switch from upadacitinib 30 mg QD to 15 mg QD (hereafter referred to as "dose switch") and change of study length from up to 5 years to 260 weeks. Updated throughout the SAP to replace "ABT-494" with "upadacitinib."
2. Updated Section 7.0. To clarify analysis details and incorporate additional summary of dose switch.
3. Updated Section 8.1. Study drug exposure groups to accommodate dose switch.
4. Updated Section 9.1.1 and Section 9.3. To incorporate handling of dose switch for long-term efficacy analysis.
5. Updated Section 9.1.2. To describe the missing data handling approach for the additional sensitivity analysis using longitudinal models for long-term efficacy.
6. Updated Section 9.3. To incorporate the additional sensitivity analysis for long-term efficacy.
7. Added language to clarify analysis details in Section 10.2.1.1, Section 10.2.1.6, Section 10.2.2.1, Section 10.2.2.3, Section 10.3.3.2, and Section 10.4.3.
8. Updated Section 10.2.1.6, and Section 10.4.1. To align with the latest upadacitinib AESI definitions in PSSAP V4.0.

9. Updated Section 10.1., Section 10.2.2, Section 10.3.3.1 Section 10.3.3.2 Section 10.3.3.3 and Section 10.4.3 to incorporate handling of dose switch for long-term safety analysis.
10. Added Appendix B to describe analysis accounting for impact of COVID-19 pandemic.
11. Added Section 11.0 for summary of changes and Section 12.0 for SAP version history summary.

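### Period 1 laboratory and vital-sign changes are tested without the baseline value as a covariate; a supplementary ANCOVA would be more precise at almost no cost

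*SAP*

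**What the plan says.** SAP 10.3.2.1 covers the longitudinally measured laboratory variables in Period 1, by visit and by as-treated group. It tabulates "sample size, baseline mean, visit mean, and the mean, standard deviation, and median of the changes from baseline" and then adds a test: "An ANOVA model with treatment as a factor will be used to test statistical significance". SAP 10.4.2 has the same plan for vital signs: "An ANOVA model with treatment as factor, will be used to test statistical significance". Neither section lists another model term, a dose-versus-placebo estimate or a confidence interval.

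The efficacy models differ. For DAS28 and HAQ-DI, SAP 9.2.3 says: "Specifically, the ANCOVA model will include treatment as the fixed factor, and the corresponding baseline value". The mixed model for the other continuous endpoints (SAP 9.1.2 and 9.2.4) also carries the baseline measurement.

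Three further statements set the weight of the point:
- Protocol 8.1.5.1 says that "clinical laboratory values will be analyzed in a descriptive manner", and its sentence also covers vital signs.
- SAP 9.2.5 limits its error control: "The overall type I error rate of the primary and ranked key secondary endpoints for the two doses will be strongly controlled".
- SAP 11.1 records that "The primary efficacy analysis and Period 1 reporting have been completed under the SAP version 2.0", and that the present version governs only later long-term reporting.

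**The concern.** Change from baseline is usually negatively correlated with baseline: subjects who start high tend to fall and those who start low tend to rise. A model with treatment alone assumes that a unit of baseline carries over fully to follow-up. Where the true slope is below 1, the unexplained part stays in the error term, and part of any chance baseline difference between groups stays in the treatment contrast. The SAP deals with this for efficacy and gives no reason for treating the safety variables differently, although their baseline values are collected and tabulated.

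Mean change is a useful place to look for a dose-related shift in this program. Protocol 3.0 reports that mean hemoglobin fell at the higher Phase 2 doses while staying within the normal range. A shift of that kind may not show in counts of Grade 3 or 4 values. Anemia, neutropenia, lymphopenia, raised creatinine, raised transaminases and raised CPK are adverse events of special interest in Protocol 6.1.1.3, so precision on the related laboratory means is worth having.

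**Working it through.** **The plan's own figure.** The documents give no power, standard deviation (SD) or correlation for any laboratory or vital-sign variable, so there is no figure to reproduce for these tests. The sample-size statement in SAP 4.3 (at least 90% power) does reproduce: 96.3% for ACR20 and 99.5% for LDA with 180 evaluable per arm. It does not bear on this point.

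**Inputs.** There are 200 subjects per dose and 100 + 100 = 200 on combined placebo (SAP 4.2). The tests below are two-sided at 0.05, which is assumed because the SAP sets no level for them. The SD is taken as equal at baseline and follow-up, and results are in SD units. The correlation rho is assumed, from 0.5 to 0.9.

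**Formulas.** With n per arm:
- ANOVA on change: variance of the contrast = 2(1−rho) × 2/n.
- ANCOVA: variance of the contrast = (1−rho²) × 2/n.
- Ratio ANCOVA/ANOVA = (1−rho²) / [2(1−rho)] = (1+rho)/2.
- With a baseline difference D between groups, the change contrast is shifted by −(1−rho)D, against the direction of the imbalance.

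If the SDs differ (s1 at baseline, s2 at follow-up), the per-subject variance of change minus the ANCOVA residual variance is (s1 − rho·s2)². This is never negative, so at this sample size ANCOVA is essentially never less precise.

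**Results at n = 200 per arm.** The square root of 2/200 is 0.10, so one standard error (SE) of baseline imbalance is 0.10 SD.

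| rho | Variance ratio | CI narrower by | SE, ANOVA | SE, ANCOVA | 80% power becomes | Shift from D = 0.10 SD |
|---|---|---|---|---|---|---|
| 0.5 | 0.75 | 13% | 0.100 | 0.087 | 89.9% | −0.05 SD |
| 0.7 | 0.85 | 8% | 0.077 | 0.071 | 86.0% | −0.03 SD |
| 0.8 | 0.90 | 5% | 0.063 | 0.060 | 84.0% | −0.02 SD |
| 0.9 | 0.95 | 3% | 0.045 | 0.044 | 82.0% | −0.01 SD |

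The difference detectable with 80% power is about 2.80 × SE. It moves from 0.28 to 0.24 SD at rho 0.5, and from 0.18 to 0.17 SD at rho 0.8.

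**Simulation under no treatment effect** (20,000 trials per rho). The ANOVA on change rejected in 4.9% of trials at rho 0.5 and 5.0% at rho 0.8. The empirical variance ratios were 0.752 and 0.895, which match the formula. Among the roughly 5% of trials with a baseline imbalance beyond 1.96 SE, the ANOVA rejected in about 18% (rho 0.5) and 10% (rho 0.8), against about 4% for ANCOVA.

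**How often that would arise.** SAP Table 9 lists 11 hematology variables and 22 chemistry variables, or 32 in all without the reflex-only INR. For one dose against placebo, 32 × 0.05 = 1.6 variables would be expected to show an imbalance of that size by chance.

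**The case against.** The strongest reply is that changing these sections now would alter no output. The ANOVA appears only in the Period 1 sections. The long-term sections (SAP 10.3.3.1 and 10.4.3) give summary statistics and no such test, and Period 1 is already reported. Replacing its pre-specified model after the unblinded Week 12 analysis would be a post hoc change. This stands. It rules out a replacement but not a supplementary analysis.

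The second reply is that the Protocol calls these analyses descriptive and that safety detection does not rest on them. The SAP also has grade shift tables, Grade 3 and 4 counts with Fisher's exact tests, liver thresholds, and risk differences with confidence intervals for events of special interest. This lowers the stakes. It does not remove the point, because the SAP still specifies significance tests of mean change. If description is the aim, an adjusted difference with its interval serves it better than a p-value alone.

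The third reply is that the gain is assumed and may be small. That is fair: at rho 0.9 it is 5% of variance.

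A reader might also infer that these laboratory tests are tests of the adverse events of special interest. They are not. Those events are identified by MedDRA queries or adjudication (SAP Table 8), and lipids, although raised in Phase 2, are not on the list in either document.

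**Conclusion.** The point holds as a free improvement with modest impact. The Period 1 laboratory and vital-sign models omit a covariate that is already in hand and that the efficacy models use. On an assumed rho of 0.5 to 0.9 with equal SDs, fitting it would cut the variance of each contrast by 25% down to 5%, and would remove the −(1−rho) share of chance baseline imbalance that now remains.

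Three stronger readings are tempting and are not supported:
- *Baseline is ignored.* It is not: the response is change from baseline, and the baseline mean is tabulated. The weakness is a slope fixed at 1 instead of estimated.
- *The tests are invalid or have inflated error.* They hold about 5% over randomization. The excess appears only conditional on a large observed imbalance. The groups are as-treated, but SAP 10.1 expects no protocol-defined switching in Period 1, so they should be close to the randomized groups.
- *Long-term safety or efficacy conclusions are affected.* The long-term mean changes are not tested this way, and the efficacy models already include baseline.

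**What to change.** Run a supplementary ANCOVA on the existing Period 1 data for the variables in SAP 10.3.2.1 and 10.4.2: change from baseline on treatment, with that variable's baseline value as covariate, by visit. Report the adjusted mean difference of each dose from combined placebo with its 95% confidence interval. Label it as supplementary and specified after Period 1 reporting, present it beside the reported ANOVA, and leave the ANOVA results unchanged. Editing the two Period 1 sections alone would not be enough, because the current SAP version governs only long-term reporting.

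The cost is one more model term in an existing program, a short written specification and an additional set of tables. No new data are needed.

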#### 10.3.2.2 Assessment of Shift from Baseline in Clinical Laboratory Variables

The baseline and post-baseline laboratory observations will be categorized as Grade 1, Grade 2, Grade 3, and Grade 4 according to OMERACT criteria (Rheumatology Common Toxicity Criteria v.2.0). For creatine phosphokinase and creatinine NCI CTC criteria will be used.

For each laboratory variable, shift tables will be generated that cross tabulate the subjects' as deemed appropriate by "as treated" treatment group:

- Category of the baseline value versus category of the final value.
- Category of the baseline value versus maximum category.
- Category of the baseline value versus minimum category.

Note that the minimum/maximum category is used, rather than the category of the minimum/maximum value. The two may be different due to variation in the reference range.

No statistical tests will be performed for this analysis.

#### **10.3.2.3 Assessment of Potentially Clinical Significant Laboratory Variables**

The criteria for potentially clinically significant laboratory values will be determined by OMERACT criteria of Grade 3 or 4. For creatine phosphokinase and creatinine, NCI CTC criteria will be used.

The number and percentage of subjects meeting the criteria for potentially clinically significant laboratory values will be summarized by "as treated" treatment group and overall. Comparisons of the percentage of subjects experiencing a value meeting the criteria between treatment groups will be performed using Fisher's exact tests. Only p-values  $\leq 0.100$  when rounded to three digits will be presented.

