 10. Systemic use of known strong cytochrome P450 (CYP) 3A inhibitors or strong CYP3A inducers from Screening through the end of the study (refer to Table 1 for examples of commonly used strong CYP3A inhibitors and inducers).
 11. Receipt of any live vaccine within 4 weeks prior to the first dose of study drug, or expected need of live vaccination during study participation including at least 4 weeks after the last dose of study drug.
 12. History of any malignancy except for successfully treated NMSC or localized carcinoma in situ of the cervix.
 13. History of clinically significant (per Investigator's judgment) drug or alcohol abuse within the last 6 months.
 14. History of gastrointestinal perforation or a history of associated gastrointestinal diseases including but not limited to diverticulitis and gastroduodenal ulcers.
 15. Conditions that could interfere with drug absorption including but not limited to short bowel syndrome.
 16. Subject has been a previous recipient of an organ transplant.
 17. History of clinically significant medical conditions or any other reason that in the opinion of the Investigator would interfere with the subject's participation in this study or would make the subject an unsuitable candidate to receive study drug.
 18. Infection(s) requiring treatment with parenteral anti-infectives within 30 days, or oral anti-infectives within 14 days prior to the first dose of study drug.
 19. History of an allergic reaction or significant sensitivity to constituents of the study drug (and its excipients) and/or other products in the same class.

20. Laboratory values meeting the following criteria within the Screening period prior to the first dose of study drug:
- Serum aspartate transaminase (AST) $> 2 \times$ ULN;
 - Serum alanine transaminase (ALT) $> 2 \times$ ULN;
 - Estimated glomerular filtration rate (GFR) by simplified 4-variable Modification of Diet in Renal Disease (MDRD) formula < 40 mL/min/1.73 m²;
 - Total white blood cell (WBC) count $< 2,500/\mu\text{L}$;
 - Absolute neutrophil count (ANC) $< 1,500/\mu\text{L}$;
 - Platelet count $< 100,000/\mu\text{L}$;
 - Absolute lymphocyte count $< 850/\mu\text{L}$;
 - Hemoglobin < 10 g/dL.

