8.1.5.3 Analysis of Laboratory, Vital Sign, and ECG Data

Changes from baseline by visit, and changes from baseline to minimum value, maximum value, and final values in continuous laboratory data, and vital signs will be summarized by treatment group.

Baseline values are defined as the last non-missing measurements recorded on or before the date of the first dose of study drug in Period 1.

The laboratory data will be categorized as Grade 1, Grade 2, Grade 3, and Grade 4 according to OMERACT criteria (Rheumatology Common Toxicity Criteria v.2.0). For creatine phosphokinase and serum creatinine, NCI CTC criteria will be used. The shift tables will tabulate the number and percentage of subjects with baseline and post-baseline values by grade level.

Listings will be provided for potentially clinically significant laboratory values and vital signs.

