### **10.3.3.2 Assessment of Potentially Clinical Significant Laboratory Values**

Long-term laboratory data will be summarized based on the number and percentage of subjects meeting the criteria for potentially clinical significant laboratory values and by the actual treatment received at the time of the event occurrence. Starting with Amendment 6, all subjects will receive open-label upadacitinib 15 mg QD, including those currently on upadacitinib 30 QD. The treatment groups for summarizing potentially clinical significant laboratory values are the same as the ones for long-term AE analysis as described in Section 8.1 and Section 10.2.2. A subject can be counted under different treatment groups if he/she switched treatment and experienced potentially clinical significant laboratory values under different treatment groups.

In the evaluation of potentially clinically significant laboratory values, the baseline value will be determined by the last non-missing measurement recorded on or before the date of the first dose of study drug in the corresponding treatment group (which may be different than the first dose of study drug received in the study). For example, for a subject who started on Placebo and switched to upadacitinib 15 mg QD, lab values under upadacitinib 15 mg QD exposure would be evaluated against the baseline value defined as the last non-missing measurement recorded on or before the date of the first dose of upadacitinib 15 mg QD. For subjects who switched from upadacitinib 30 mg QD to upadacitinib 15 mg QD, lab values under upadacitinib 15 mg QD exposure would still be evaluated against the baseline defined based on the first dose of upadacitinib 30 mg QD.

A listing of all subjects with any laboratory determination meeting OMERACT criteria of Grade 3 or 4 will be provided by Grade. For creatine phosphokinase and creatinine, NCI CTC criteria will be used. For each of these subjects, the whole course of the respective parameter will be listed.

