J2. Cough	Transient, intermittent, occasional OTC meds relieve	Persistent, requires narcotic or other prescription meds for relief	Recurrent, persistent coughing spasms without consistent relief by meds, interferes with function	Interferes with oxygenation; debilitating

J3. Dyspnea	Subjective, transient, no interference with function	Symptomatic, intermittent or recurring, interferes with exertional activities	Symptomatic during daily routine activities, interferes with function, treatment with intermittent nasal O 2 relieves	Symptomatic at rest, debilitating, requires constant nasal O 2
J4. Pleuritic pain (pleurisy)	Transient, intermittent symptoms, no treatment or OTC meds relieve	Persistent symptoms, requires prescription meds for relief	Prolonged symptoms, interferes with function, requires frequent narcotic pain relief	Debilitation, requiring hospitalisation
J5. Pneumonitis (pulmonary infiltrates)	Asymptomatic radiographic changes, transient, no treatment required	Symptomatic, persistent, requiring corticosteroids	Symptomatic, requiring treatment including O 2	Debilitating, not reversible; or requiring assisted ventilation
J6. Pulmonary function decreased (FVC or carbon monoxide diffusion capacity – DLCO)	76% – 90% of pre-treatment value	51% – 75% of pre-treatment value	26% – 50% of pre-treatment value	≤ 25% of pre-treatment value
Laboratory Data				
K. Haematology				
K1. Hgb (g/dl) decrease from pre-treatment	1.0 – 1.4	1.5 – 2.0	2.1 – 2.9, or Hgb < 8.0, > 7.0	≥ 3.0; or Hgb < 7.0
K2. Leukopenia (total WBC) × 1000	3.0 – 3.9	2.0 – 2.9	1.0 – 1.9	< 1.0
K3. Neutropenia (× 1000)	1.5 – 1.9	1.0 – 1.4	0.5 – 0.9	< 0.5
K4. Lymphopenia (× 1000)	1.5 – 1.9	1.0 – 1.4	0.5 – 0.9	< 0.5
K5. Platelets (× 1000)	75 – LLN	50 – 74.9	20 – 49.9; platelet transfusion required	< 20; recurrent platelet transfusions

L. Chemistry				
L1. Hypercalcaemia (mg/dl)	1.1 × ULN – 11.5	11.6 – 12.5	12.6 – 13.5; or symptoms present	> 13.5; or associated coma
L2. Hyperglycemia (mg/dl) Fasting	140 – 160	161 – 250	251 – 500	> 500, or associated with ketoacidosis
L3. Hyperkalaemia (mmol/l)***	5.5 – 5.9	6.0 – 6.4	6.5 – 7.0 or any ECG change	> 7.0 or any arrhythmia
L5. Hypocalcaemia (mg/dl)	0.9 × LLN – 7.8	7.7 – 7.0	6.9 – 6.5; or associated with symptoms	< 6.5 or occurrence of tetany
L6. Hypoglycemia (mg/dl)	55 – 64 (no symptoms)	40 – 54 (or symptoms present)	30 – 39 (symptoms impair function)	< 30 or coma

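### The long-term count of potentially clinically significant laboratory values (SAP 10.3.3.2) requires no worsening from baseline, so a subject already in Grade 3 lymphopenia at entry can be counted as an on-treatment case

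*SAP*

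**What the plan says.** SAP 10.3.2.3 sets the criterion for Period 1: "The criteria for potentially clinically significant laboratory values will be determined by OMERACT criteria of Grade 3 or 4". NCI CTC grades replace OMERACT for creatine phosphokinase and creatinine. The section adds: "Comparisons of the percentage of subjects experiencing a value meeting the criteria between treatment groups will be performed using Fisher's exact tests".

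SAP 10.3.3.2 uses the same criterion for the long-term data: "Long-term laboratory data will be summarized based on the number and percentage of subjects meeting the criteria". It then says: "In the evaluation of potentially clinically significant laboratory values, the baseline value will be determined by the last non-missing measurement". That baseline is the one before the first dose in the corresponding treatment group. Subjects who moved from 30 mg to 15 mg keep the baseline from before their first 30 mg dose. The section also lets one subject count under several treatment groups. It has no sentence saying that a qualifying value must be worse than baseline.

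Other relevant places:
- Protocol 5.2.2, criterion 20, excludes an absolute lymphocyte count below 850/µL during the Screening period.
- SAP Appendix A, item K4, grades lymphopenia on the count alone: Grade 2 is 1.0–1.4, Grade 3 is 0.5–0.9 and Grade 4 is below 0.5 (× 1000/µL).
- SAP Table 10 requires blood pressure to cross a threshold and also to change from baseline. Weight is defined purely as change.
- SAP 11.1 says that Period 1 reporting was completed under version 2.0 and that version 3.0 governs only later long-term reporting.

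**The concern.** A table of potentially significant values by treatment received is read as what happened on that treatment. For a parameter graded on its absolute level, the rule as written does not separate a subject who fell into Grade 3 on drug from one who was there before the first dose and stayed there. A baseline is defined with care but has no stated effect on the count for such parameters, so two programmers could produce different tables from the same text.

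At stake is the reported percentage of subjects with Grade 3/4 lymphocyte values in each exposure group, and how those percentages compare. Because a subject may be counted under each treatment received, the same pre-drug status can appear more than once.

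**Working it through.** **Step 1. Can an eligible subject start in Grade 3?** Compare each entry limit (Protocol 5.2.2, criterion 20) with the Grade 3 range (SAP Appendix A).

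| Parameter | May enter at | Grade 3 | Overlap |
|---|---|---|---|
| Lymphocytes (× 1000/µL) | ≥ 0.85 | 0.5–0.9 | 0.85–0.90 |
| Neutrophils (× 1000/µL) | ≥ 1.5 | 0.5–0.9 | none |
| White cells (× 1000/µL) | ≥ 2.5 | 1.0–1.9 | none |
| Platelets (× 1000/µL) | ≥ 100 | 20–49.9 | none |
| Haemoglobin, absolute part (g/dL) | ≥ 10 | < 8.0 | none |
| AST (× ULN) | ≤ 2 | 3.1–8.0 | none |
| ALT (× ULN) | ≤ 2 | 3.0–8.0 | none |

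Among these, only lymphocytes overlap. The band reaches just under 1.0 if values in the unassigned gap between 0.9 and 1.0 are graded 3. A baseline value can also lie below 850/µL, because the limit applies to Screening, whereas Protocol 8.1.5.3 says: "Baseline values are defined as the last non-missing measurements recorded on or before the date of the first dose of study drug in Period 1". Glucose and creatine phosphokinase have no entry limit in criterion 20, so the same question arises there, but the documents give nothing to size it. Haemoglobin and creatinine grades are partly relative to baseline and are less affected.

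**Step 2. What does the rule do with such a subject?** Take a baseline of 870/µL and a later value of 880/µL. Both are Grade 3. The subject meets the criterion although the count rose slightly. Under the groups in SAP 8.1, a subject who goes from placebo to 30 mg to 15 mg can be counted under placebo, under 30 mg, and under 15 mg after the switch.

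**Step 3. How large could it be?** The documents give neither the share in Grade 3 at baseline nor the new-onset rates, so these inputs are assumptions:
- b = share in Grade 3 at baseline: 2%, 5% or 10%
- q = share of those with a Grade 3/4 value again later: 50% or 80%, the same in both groups
- p = new onset in the others: 3% on placebo, 9% on upadacitinib

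Count as written = b·q + (1 − b)·p. Count of new onset only = (1 − b)·p, with a ratio of 3.0 throughout. For b = 5% and q = 50%, the placebo figure as written is 0.025 + 0.95 × 0.03 = 5.35%, against 2.85% for new onset.

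| b | q | Placebo, as written | Upadacitinib, as written | Ratio | Carried-over share of placebo count |
|---|---|---|---|---|---|
| 2% | 50% | 3.9% | 9.8% | 2.5 | 25% |
| 2% | 80% | 4.5% | 10.4% | 2.3 | 35% |
| 5% | 50% | 5.3% | 11.0% | 2.1 | 47% |
| 5% | 80% | 6.9% | 12.6% | 1.8 | 58% |
| 10% | 50% | 7.7% | 13.1% | 1.7 | 65% |
| 10% | 80% | 10.7% | 16.1% | 1.5 | 75% |

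With q equal in both groups, the difference in percentage points does not change: it is (1 − b) × 6 points on either count. The ratio and the absolute levels are what move.

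**Step 4. Effect on a test, for illustration.** Exact Fisher power (two-sided 0.05, 200 per group) at 3% versus 9% is 66% with no baseline carriers. With carriers counted it is 55–58% at b = 2%, 42–48% at 5% and 30–36% at 10%. The new-onset count would itself sit slightly below 66%, because its rates are multiplied by 1 − b. A harsher set of assumptions, 6% versus 1% with every carrier persisting, gives 73.5% with no carriers and 50.9%, 33.9% and 25.6% at 2%, 5% and 8%. SAP 10.3.3.2 plans no test, so none of these figures describes an analysis that is still open.

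**The case against.** The defence has several sound points.

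- **Period 1 is closed.** The Fisher comparison sits in 10.3.2.3 and has been reported. A reader might infer from Step 4 that the trial still stands to lose that power. It does not, because the long-term table is descriptive.
- **A baseline is already named.** SAP 10.3.3.2 says values are judged against it, and a reader might take that to imply worsening. The text does not say so. For a grade set by the count alone, the baseline changes nothing unless a rule is added.
- **Randomisation balances carriers.** A reader might suspect bias toward one arm. Nothing in the documents supports that; the effect is inflation and dilution.
- **Adverse events of special interest are separate.** Lymphopenia is on that list, but SAP Table 8 identifies it by a query of reported adverse events, and SAP 10.2 requires onset after the first dose. Inflated rates there do not follow.
- **The information survives.** The long-term listing shows the whole course of the parameter for each Grade 3/4 subject. SAP 10.3.3 plans no shift table, but Protocol 8.1.5.1 plans laboratory shifts and covers both periods combined. It would be wrong to say that long-term shifts were never planned.
- **An inclusive count is safer.** Requiring a higher grade would drop a fall from 870 to 550/µL, a real decline within Grade 3. This stands, and the fix must allow for it.

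These points limit scope and weight. They leave the headline percentage mixing status before drug with change on drug.

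**Conclusion.** The point holds for the long-term table. As written, SAP 10.3.3.2 counts a subject already in Grade 3 before drug as an on-treatment case whenever a later value is again Grade 3 or 4, and can do so under more than one treatment group. The clear case is lymphocytes, in the band from 850 to 900/µL at entry.

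The direction is certain: absolute percentages rise and relative contrasts shrink. The size is unknown. Under the Step 3 assumptions, the placebo percentage is 1.3–1.5 times the new-onset figure at 2% carriers (3.94/2.94 to 4.54/2.94) and 1.9–2.4 times at 5% (5.35/2.85 to 6.85/2.85). Those multiples depend on the assumed new-onset rate, and a lower rate would give larger ones. The Period 1 results are not reopened. This is a cheap improvement worth making before the final long-term report.

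**What to change.** In SAP 10.3.3.2:

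1. Make the main count subjects with a post-baseline Grade 3/4 value whose grade is higher than at the baseline already defined there for each treatment group.
2. Show in a separate row the subjects already Grade 3/4 at that baseline and, among them, those whose value fell further within the grade.
3. Keep the any-Grade-3/4 total alongside, so that the inclusive figure remains visible.
4. Tabulate long-term shifts from baseline, which Protocol 8.1.5.1 already plans and SAP 10.3.3 omits.

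The main count needs one sentence of SAP text and one programming condition. The extra rows and shift tables use data already collected. The price is a slightly longer table. Subjects who stay in their baseline grade leave the main count but remain in the separate rows and in the listing. Section 10.3.2.3 needs no change for results already reported.
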